7.3. Data entry

Data collected during this study will be maintained in the subject's source document folder. For the purposes of data analyses, data from the source will be entered into a database or spreadsheet on a designated, password-protected study computer. The subject ID will be entered, not the subject name. Data on the computer will be password-protected and only accessible to the Investigator and delegated study staff members.

7.4. Subject withdrawals

The Investigator or subjects themselves may stop study treatment at any time for safety or personal reasons.

No replacement of subjects who drop out or are withdrawn following administration of testosterone therapy will take place. Subjects who, having been randomized, do not initiate testosterone therapy may be replaced. The replacement subject will start the study from the beginning.

7.5. Stopping rules

The stopping criteria for an individual patient will be:

- Serum total testosterone concentration >1750 ng/dL on two consecutive blood draws
- Hematocrit >54%
- Elevation of one or more liver enzymes >2X upper reference threshold
- Development of subjective and objectively confirmed gynecomastia
- New onset pedal/ankle edema >1+ on a 1-4 scale
- Report of any serious adverse outcomes, including heart attack, heart failure, stroke, depression, hostility, aggression, liver toxicity, male infertility (in accordance with U.S. Food and Drug Administration (FDA) recommendations)
- Report of any withdrawal symptoms associated with abuse of high doses of testosterone, including depression, fatigue, irritability, loss of appetite, decreased libido, insomnia (in accordance with U.S. Food and Drug Administration (FDA) recommendations)
- New onset of prostate cancer (in accordance with U.S. Food and Drug Administration (FDA) recommendations)

8. Data analysis and statistical considerations

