T deficiency is often treated with testosterone therapy of which various delivery methods are available³. Treatment is aimed at inducing and maintaining secondary sex characteristics and improving sexual function, sense of well-being, and bone mineral density⁴. Although testosterone was first synthesized in 1935, treatment options are continually evolving⁵.

One standard treatment for TD is intramuscular (IM) injections of exogenous T⁶. However, subcutaneous (SQ) injections may have some advantages compared to IM injections. SQ injections is more convenient and less challenging than IM for men who are candidates for self-injection. SQ also involves a smaller needle and may be less intimidating to patients. This trial will investigate how serum testosterone levels are affected by the route of T administration.

1.2. **Rationale and hypothesis**

The purpose of this study is to preliminarily determine if the route of delivery of testosterone therapy affects testosterone concentrations in men. Our hypothesis that SQ will provide comparable or acceptable T concentrations as IM, with regard to duration of action and peak or average concentrations.

2. Objectives

2.1. **Primary outcome and endpoint (endpoint bulleted below)**

The primary objective of this study is to determine how testosterone concentration in men differs based on administration route for T injections in men.

The Primary endpoints are total testosterone concentration and calculated free T concentration following injection, measured by Beckman assays and equipment.

2.2. **Secondary outcomes and endpoints (endpoints bulleted below)**

The Secondary endpoints are responses to Low Testosterone Questionnaire, International Prostate Symptom Scores, and levels of estradiol, LH, FSH, SHBG, and PSA following injection, measured by Beckman assays and equipment and hematocrit following injection measured by Quest Diagnostics.

3. Study design

In this single-center clinical trial, 20 subjects being treated with testosterone therapy for T deficiency will be randomized to subcutaneous testosterone injection followed by intramuscular testosterone injection or intramuscular testosterone injection followed by subcutaneous testosterone injection. Subjects will be screened for eligibility and subsequently randomized at the baseline visit, then followed for four weeks.

4. Study population

4.1. **Inclusion criteria**

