6.3. Recruitment and consent

A member of the study staff will explain study procedures in detail to the potential subject. The study staff member will clearly outline that the purpose of the study is to compare the testosterone concentrations following two different routes of testosterone therapy. While any study staff member may conduct the informed consent discussion and obtain informed consent, a study physician will be available at all times for any consent-related questions. Undue coercion will be prevented by stressing that participation in this study is voluntary and the future care of the potential subject will not be affected by his decision regarding participation in this study.

7. Activities and measurements

Subjects planning to initiate testosterone treatment via injection at MHB will be consented into the study. Upon enrollment in the study, the randomization will be completed for each subject.

Blood collection will occur before each injection. Subjects will rate pain on the Likert scale following each injection. After treatment with the first mode of T administration (SQ or IM depending on randomization), subjects will come in for blood draws 3 days and 7 days following the injection. Two weeks after the initial injection, subjects will come in for treatment with the second mode of T administration (SQ or IM depending on randomization). Subjects will come in for blood draws 3 days and 7 days following the second injection. Two weeks after the second injection, subjects will complete an end of study assessment with an Investigator and will complete a survey assessing their satisfaction with treatment. Subjects will likely continue testosterone therapy at Men's Health Boston after completion of the study.

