7.2. Blood sample collection

At each visit, up to 14mL (approximately 3 teaspoons) of blood will be collected for study purposes. The serum samples (approximately 6mL) will be frozen and shipped to Beckman Coulter for analysis. Whole blood samples (approximately 3mL) will be sent to Quest Diagnostics for analysis.

	At each visit	Total for study
Total amount collected for study	13mL (4 teaspoons)	91mL
Amount of serum shipped to Beckman	6mL	42mL
Amount of whole blood for Quest	4mL	28mL

The Investigator will review all laboratory test results. Laboratory test results that are considered clinically significant by the Investigator will be followed to satisfactory resolution. Laboratory abnormalities are considered to be adverse events only if they result in discontinuation from the study, necessitate therapeutic medical intervention, and/or if the Investigator considers them to be an adverse event.

Beckman Coulter will arrange for samples to be tested for this study. Contact information is listed below:

Name:	[name] Staff Clinical Studies Scientist Beckman Coulter, Inc.
Address:	Immunoassay Business Center [name]
[contact]
Email:	[contact]

Quest will analyze whole blood samples for this study. Contact information is listed below:

Name:	Quest Diagnostics
Address:	[name]
[contact]

Sample collection

Seven blood samples will be obtained throughout the study. Samples will be collected at the following visits:

- Visit 1
- Visit 2
- Visit 3
- Visit 4
- Visit 5
- Visit 6
- End of Study

Sample processing and storage

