Whole blood samples from the SST tubes (10mL) will be spun down and resulting serum (6mL) will be transferred to an aliquot tube. Aliquot tubes will be frozen at the site for batch shipping. Whole blood samples from the EDTA tubes (4mL) will remain ambient and will be collected at the site for analysis by Quest Diagnostics. Remaining specimen will be disposed of in biohazard waste receptacle. Beckman Coulter samples will be labeled with a study-specific ID number, date of birth, Visit number, and collection date and time. No other identifiers will be transferred with the samples to the lab. Quest samples will be labeled with a study-specific ID number, date of birth, visit number, and collection date and time. No other identifiers will be transferred with the samples to the lab. The laboratories will not have access to the Master List that links the study-specific ID number with subject identifiers.

Frozen study samples are to be kept at -20°C with an acceptable range of -10° to -30°C. Freezers must maintain constant temperature (i.e. freezers must not be frost-free or defrost automatically). A temperature log will be maintained at the site.

Sample shipping

Frozen samples will be batch shipped at designated times to Beckman Coulter, Inc. Ambient samples will be collected by Quest after each visit.

De-identification of samples

After the master list is destroyed, samples will not be traceable back to individual subjects.

Specimen analysis

Blood sampling will be performed at MHB and analyzed by Beckman Coulter, Inc. and Quest Diagnostics, Inc. Results of the analysis will be provided to MHB and results of the tests may be discussed with subjects, as it pertains to their medical care.

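### The testosterone stopping criterion relies on frozen, batch-shipped serum, and the plan does not ensure results are back before the second and last study injection

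*Combined protocol and SAP*

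**What the plan says.** - **The rule.** Section 7.5 lists, among its stopping criteria for an individual patient, "Serum total testosterone concentration >1750 ng/dL on two consecutive blood draws". It does not say whether meeting it ends treatment, participation or both.
- **The assay.** Section 2.1: "The Primary endpoints are total testosterone concentration and calculated free T concentration following injection, measured by Beckman assays and equipment". No other post-injection testosterone assay is described.
- **The sample route.** Section 7.2: "The serum samples (approximately 6mL) will be frozen and shipped to Beckman Coulter for analysis". Under sample processing, "Aliquot tubes will be frozen at the site for batch shipping"; under sample shipping, "Frozen samples will be batch shipped at designated times to Beckman Coulter, Inc". Neither the shipping times nor a turnaround is given.
- **The contrast.** The EDTA tubes go another way: "Ambient samples will be collected by Quest after each visit". Section 2.2 has "hematocrit following injection measured by Quest Diagnostics". One laboratory criterion in 7.5 therefore has a visit-by-visit sample route, and the testosterone criterion has a batch route.
- **The dosing calendar.** Section 7: "Two weeks after the initial injection, subjects will come in for treatment with the second mode of T administration". Blood is drawn before each injection and again 3 and 7 days after it. No study injection follows the second one.

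**The concern.** A criterion that can withhold a study injection works only if the result is known before that injection. The plan describes holding samples for batches as its procedure and says nothing to make testosterone values available by Visit 4. Followed as written, it allows a man who met the criterion in the first period to receive his second injection before anyone has seen the values.

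There is a smaller consequence for the data. Whether such a man contributes a second period could depend on the shipping calendar, in a 20-man crossover where section 7.4 does not replace men who withdraw after dosing.

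**Working it through.** **Plan's own figure.** The plan gives no timing figure to reproduce. The 80% power in section 8.1 is not an input here.

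**Step 1: which pairs of draws can act before the second injection?** Inputs are the visit days (0, 3, 7, 14, 17, 21, 28) from the schedule of activities and the second injection on Day 14. Lead time = 14 minus the day of the second draw in the pair.

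| Pair (days) | Lead time (days) | Can it affect study dosing? |
|---|---|---|
| 0 / 3 | 14 − 3 = 11 | Not realistically: Day 0 precedes treatment, in men whose entry value was below 350 ng/dL (section 4.1) |
| 3 / 7 | 14 − 7 = 7 | Yes, if the results are back |
| 7 / 14 | 14 − 14 = 0 | No: the second sample is taken at the injection visit and then frozen |
| 14 / 17 | 14 − 17 = −3 | No: after the last study injection |
| 17 / 21 | 14 − 21 = −7 | No |
| 21 / 28 | 14 − 28 = −14 | No |

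**Step 2: the time available.** With windows of ± 2 days, Visit 3 falls on Days 5 to 9 and Visit 4 on Days 12 to 16. The shortest gap is 12 − 9 = 3 days, the nominal gap 14 − 7 = 7 days, and the longest 16 − 5 = 11 days. The Day 3 aliquot is collected earlier, so the Day 7 aliquot sets the limit.

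**Step 3: an illustration.** The documents give neither a batch interval nor a turnaround, so both are assumed: batches every W = 7, 14 or 28 days, and L = 2 to 4 days from dispatch to report. If Visit 3 falls at a random point in the batch cycle, the wait for dispatch is uniform on 0 to W, and

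P(result in time) = (gap − L) / W, held between 0 and 1.

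| W | Gap 7, L = 4 | Gap 7, L = 2 | Gap 3, L = 4 (worst) | Gap 11, L = 2 (best) |
|---|---|---|---|---|
| 7 | 3/7 = 43% | 5/7 = 71% | −1/7, so 0% | 9/7, so 100% |
| 14 | 3/14 = 21% | 5/14 = 36% | 0% | 9/14 = 64% |
| 28 | 3/28 = 11% | 5/28 = 18% | 0% | 9/28 = 32% |

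A single batch at the end of the study gives 0%. At the nominal gap, even weekly batches would miss the injection in 29 to 57% of cases (100 − 71 and 100 − 43).

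**The case against.** A reader might infer that sections 7.2 and 7.5 contradict each other, or that batch shipping makes the rule unworkable. The documents do not support either reading. The shipping times are undefined and could be set to fall before each man's Visit 4. On the assumed figures above, the chance of a timely result reaches 71% at the nominal gap and 100% at the longest. The gap in the plan is a missing guarantee.

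A reader might also infer that a late result has no use. That goes too far as well. Section 7 expects most men to stay on testosterone at the same clinic, so a late value could inform that care, and it could end the remaining study visits. The limitation concerns study injections only.

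Other provisions count in the plan's favour. The Investigator reviews all laboratory results and follows up the clinically significant ones (7.2). Results return to the clinic (7.2). Treatment can be stopped on safety grounds whenever needed (7.4). Adverse events are assessed at Visits 2, 3 and 4 (7.1). Testosterone is one of eight criteria in 7.5. All of this stands, but none of it fixes when a testosterone value arrives, and review cannot precede receipt.

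Finally, the percentages measure lateness, not harm. The documents give no basis for saying how many men would exceed the threshold on two successive draws.

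**Conclusion.** The concern holds in a limited form: the plan as written does not ensure that the testosterone criterion can operate before the second injection. The calendar result (one usable pair of draws, with 7 days nominally and 3 to 11 within the windows) follows from the documents alone. The probabilities rest on the assumed batch intervals, the assumed turnaround and a random batch phase. Their width, 0 to 100% for weekly batches across the windows, mainly shows how much the plan leaves open.

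This is more than an omitted detail, because holding for batches is the stated procedure and the same section gives the other tubes a pick-up after every visit. It is an operational and safety point; no endpoint, sample size or power figure changes.

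**What to change.** Reconcile 7.2 with 7.5 in one of two ways.

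1. Change the shipping text so that each man's Visit 2 and Visit 3 serum aliquots are shipped after Visit 3, or on collection, instead of being held for a batch, with total testosterone reported to the Investigator ahead of Visit 4. State the turnaround too. With dispatch on the day of Visit 3, an assumed 2 to 4 days fits the nominal 7-day gap, but 4 days would overrun the shortest gap of 3 days by one day.
2. Otherwise, state in 7.5 that this criterion can be applied only in retrospect.

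The first option costs about 20 × 1 = 20 extra shipments if the two aliquots travel together, or 20 × 2 = 40 if sent separately. It needs no extra visit or draw. The second costs only wording.

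Adding testosterone to the existing after-visit pick-up is less simple than it looks. That pick-up carries EDTA whole blood, the criterion is on serum, and the 6 mL of serum is allocated to Beckman.

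No view is taken on the threshold, the dose, or what should follow when the criterion is met.

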In this randomized, cross-over study 20 subjects who are undergoing testosterone (T) therapy for the treatment of T deficiency will receive both subcutaneous testosterone therapy and intramuscular testosterone therapy. One group will receive a SQ injection followed by an IM injection and one group will receive an IM injection followed by a SQ injection. The primary objective of this study is to measure testosterone concentration in men after these two treatment routes and determine if there are any significant differences due to modes of administration. Endpoints will include total serum testosterone and calculated free testosterone. A questionnaire will also be administered to assess overall patient experience with each route of administration.

Schedule of activities

	Pre-Enrollment (prior to Day 0)	Visit 1 Day 0	Visit 2 Day 3	Visit 3 Day 7	Visit 4 Day 14	Visit 5 Day 17	Visit 6 Day 21	End of Study Day 28
Window	-14 to 0 days	± 0 days	± 2 days	± 2 days	± 2 days	± 2 days	± 2 days	± 2 days
Informed consent	X							
Eligibility assessment ¹ • Laboratory testing ²	SC							
Questionnaires ³	SC	X			X			X
Testosterone Treatment • Pain rating ⁴		SC			SC			
Blood sampling • Beckman Coulter ⁵		X	X	X	X	X	X	X
End of study ⁶								

¹ Eligibility labs: use the most recent values performed as part of routine clinical care: [1] total testosterone, [2] free testosterone, [3] PSA

² Other lab data collected: use the most recent values performed as part of routine clinical care: [1] estradiol, [2] LH, [3] FSH, [4] SHBG, [5] hematocrit

³ Responses collected for: [1] Low Testosterone Questionnaire | © 2014 Men's Health Boston, [2] International Prostate Symptom Score (IPSS) | American Urological Association

⁴ Rating pain after injection on Likert scale

⁵ Samples collected for: visits 1, 4, 7: [1] total testosterone, [2] free testosterone, [3] PSA; visits 2, 3, 5, 6: [1] total testosterone, [2] free testosterone, [3] estradiol, [4] LH, [5] FSH, [6] SHBG, [7] hematocrit, [8] PSA

⁶ End of study survey – preferred mode of administration

X = Research only

SC = Standard care

Table of contents

List of abbreviations and definitions	7
1. Introduction	8
1.1 Background	8
1.2 Rationale and hypothesis.....	8
2. Objectives	8
2.1 Primary outcome and endpoint.....	8
2.2 Secondary outcomes and endpoints.....	8
3. Study design	9
4. Study population	9
4.1 Inclusion criteria	9
4.2 Exclusion criteria.....	9
4.3 Protected populations	9
5. Trial interventions	10

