Each patient must meet all of the following inclusion criteria to be enrolled in the study. For laboratory assessment, use the most recent values performed as part of routine clinical care.

- 1) Ability to read, write, and understand English
- 2) Age greater than or equal to 18
- 3) Diagnosed with testosterone deficiency
- 4) Pre-enrollment testosterone concentration of less than 350 ng/dL
- 5) Planning to initiate testosterone treatment at MHB
- 6) Willing to be followed at MHB for at least one month
- 7) Willing to provide informed consent for this study

4.2. **Exclusion criteria**

Patients meeting any of the following exclusion criteria are not to be enrolled in the study. For laboratory assessment, use the most recent values performed as part of routine clinical care.

- 1) Previous exposure to exogenous T, clomiphene citrate, or other Selective Estrogen Receptor Modulators, unless off therapy for at least 12 weeks
- 2) American Urological Association Prostate Symptom score of 15 or greater or significant prostatic symptoms
- 3) History of carcinoma, tumors or induration of the prostate or the male mammary gland, including suspicion thereof
- 4) Pre-enrollment serum PSA more than 4 ng/ml
- 5) Serious psychiatric disease or uncontrolled medical illness, as suspected from the history or clinical examination
- 6) Used any sex hormones or steroidal anabolic drug supplements within 28 days before pre-enrollment testosterone collection or at any time throughout the study
- 7) Incapable of giving informed consent or complying with the protocol

4.3. **Protected populations**

Vulnerable populations will not be enrolled in this study.

5. Modes of Administration

During the study, subjects will be assigned to intramuscular injections, followed by subcutaneous injections or subcutaneous injections, followed by intramuscular injections. Subjects will already have been prescribed testosterone treatment at MHB, participation in the study will only alter the route of administration of T. Subjects will be given standard dosage for bi-weekly T injections (200mg).

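### Section 7.5 stops a subject on raised liver enzymes, but no liver enzyme is scheduled before enrollment or at any of the seven study visits

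*Combined protocol and SAP*

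**What the plan says.** Section 7.5 lists the criteria for stopping an individual patient. Three of them rest on a laboratory value: "Serum total testosterone concentration >1750 ng/dL on two consecutive blood draws", a hematocrit above 54%, and "Elevation of one or more liver enzymes >2X upper reference threshold". The section does not say which enzymes are meant, when they are to be measured or by which laboratory.

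The laboratory tests are itemized in two places that agree with each other.

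- **Pre-enrollment.** Footnote 1 to the Schedule of activities gives total testosterone, free testosterone and PSA. Footnote 2 adds "1] estradiol, [2] LH, [3] FSH, [4] SHBG, [5] hematocrit".
- **Study visits.** Footnote 5 gives total testosterone, free testosterone and PSA at Visits 1, 4 and 7. At Visits 2, 3, 5 and 6 it gives total and free testosterone and then "3] estradiol, [4] LH, [5] FSH, [6] SHBG, [7] hematocrit, [8] PSA".
- **Section 7.1** repeats these lists visit by visit.

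The secondary laboratory endpoints in section 2.2 are "levels of estradiol, LH, FSH, SHBG, and PSA following injection", plus hematocrit. The laboratory criteria in sections 4.1 and 4.2 concern testosterone and PSA.

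**The concern.** A stopping criterion stated as a laboratory threshold protects a subject only if someone measures the quantity. Here the plan sets a numerical limit on liver enzymes and provides no test that would produce the number. The ethics committee and the subjects could reasonably read section 7.5 as saying that enzymes are watched during the study, and the schedule does not do that.

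With no baseline value, an elevation found by chance during the study could not be told apart from one present before the first injection.

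What is at stake is limited. Each man receives two study injections, on Day 0 and Day 14, so the only study dose that an on-study stop can prevent is the second one, 200 mg by the other route.

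**Working it through.** The plan gives no figure on this point to reproduce. The check is a count of scheduled tests, followed by visit-window arithmetic to see where an added test would fit.

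**Step 1. Scheduled tests behind each laboratory criterion in 7.5** (Schedule footnote 5 and section 7.1; the End of Study visit is Visit 7)

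| Value used in 7.5 | Visits with the test | Study visits | Post-dose visits before second injection (Visits 2, 3) | Pre-enrollment |
|---|---|---|---|---|
| Total testosterone | 1 to 7 | 7 of 7 | 2 of 2 | yes |
| Hematocrit | 2, 3, 5, 6 | 4 of 7 | 2 of 2 | yes |
| Liver enzymes | none | 0 of 7 | 0 of 2 | no |

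The hematocrit count follows footnote 5 and section 7.1. The volume table in section 7.2 allots 4 mL of whole blood for Quest at each visit (4 × 7 = 28 mL), which could suggest hematocrit at all seven. The liver-enzyme row is the same on either reading.

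**Step 2. Could the omission come from the text extraction?** The footnotes are numbered without a break (3, 5, 3 and 8 items), section 7.1 repeats the same tests, and neither place shows a redaction. An extraction fault would have to have removed the same item from both.

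**Step 3. Does another provision supply an enzyme value?**

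- Section 7.5 also lists liver toxicity, but among serious outcomes that are reported. A report is not an enzyme measurement.
- Section 7.2 says "The Investigator will review all laboratory test results". That covers results that exist and does not order a test.
- Section 7.1 puts an adverse event assessment at every study visit, and section 7.4 lets the investigator stop treatment at any time for safety. Either could lead to a liver test, but neither requires one.

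**Step 4. Where would a test fit before the second injection?** Visits 2, 3 and 4 fall on Days 3, 7 and 14, each ± 2 days, so their windows are Days 1 to 5, 5 to 9 and 12 to 16.

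- Visit 3 to Visit 4: nominal 14 − 7 = 7 days; shortest 12 − 9 = 3; longest 16 − 5 = 11.
- Visit 2 to Visit 4: nominal 14 − 3 = 11 days; shortest 12 − 5 = 7; longest 16 − 1 = 15.

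Either visit leaves time for a result. Visit 3 allows longer exposure to the first dose but can leave only 3 days. Visit 2 always leaves at least 7.

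**Step 5. Added testing.** One post-dose visit: 20 subjects × 1 = 20 occasions, or 40 results with two enzymes. Baseline: up to 20 occasions, or 40 results, and fewer where routine care already supplies the values.

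**The case against.** The strongest reply is that a stopping criterion need not have a scheduled test behind it. Gynecomastia, edema and prostate cancer in section 7.5 have no named scheduled examination either; PSA bears only indirectly on the last. They can act through the visit assessments and the investigator's judgment, and an enzyme test ordered for clinical reasons could trigger the liver rule in the same way. The men were already prescribed testosterone, and section 5 says that "participation in the study will only alter the route of administration of T". The study lasts four weeks, and the documents show no specific liver hazard.

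Much of this stands, and it keeps the point minor. It does not remove it. Edema or breast enlargement can be noticed or reported at a visit, whereas a raised enzyme cannot be seen without a blood test. Enzymes are the only one of the three laboratory values in 7.5 that the schedule leaves out.

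A reader might also infer that the testosterone rule fails in the same way, because serum is frozen and shipped in batches and no deadline puts the Day 3 and Day 7 results before the second injection. The documents do not support that. Testosterone is measured at every visit, section 7.2 provides for results to return to the site, for investigator review and for follow-up of clinically significant values, and nothing rules out shipment before Day 14. Silence on turnaround is missing operational detail and does not show that results would come late.

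**Conclusion.** The point holds for liver enzymes. Section 7.5 states a laboratory stopping rule that the protocol's own schedule cannot trigger: 0 of 7 study visits, 0 of 2 post-dose visits before the second injection, and no baseline. It can act only on a test obtained outside the schedule.

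This is a minor participant-safety inconsistency. It has no bearing on the sample size, the error rate or the comparison of routes. The exposure concerned is one 200 mg injection, and only in a man whose enzymes pass the threshold. The documents give no frequency for that and none is estimated here. It would go too far to say that the rule could never act or that subjects face a demonstrated liver risk.

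The conclusion assumes that the itemized lists in the Schedule footnotes and section 7.1 are complete. Their agreement supports that.

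**What to change.** Add ALT and AST to the pre-enrollment labs (footnote 2 and section 7.1) and to one post-dose visit before the second injection, and require the investigator to review the result before that injection. Use Visit 3 if results can be back within the shortest gap of 3 days; otherwise use Visit 2. Name the enzymes in section 7.5. ALT and AST are a proposal, since the plan names none.

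The post-dose test can use serum from the SST tube already drawn, if volume permits. Section 7.2 sends the 6 mL of serum to Beckman and gives no minimum assay volume, so the site should confirm that some can be spared.

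If enzymes are not meant to be monitored, delete the criterion and give the reason.

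Cost: about 20 post-dose and up to 20 baseline test occasions; a laboratory route for the serum, because Quest is described only as receiving EDTA whole blood; somewhat less serum in the frozen aliquot at the chosen visit; and an amendment with written IRB approval (section 11.7). Deletion costs only the amendment.
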